3.3.3 Exclusion criteria

Patients meeting any of the following criteria cannot roll over.

1. Patients who were not compliant with key study procedures (colonoscopy, treatment compliance, endpoint assessment, contraception measures) in preceding trial 1311.6
2. Patients who could not tolerate BI 655066/ABBV-066 (risankizumab) treatment for tolerability or safety reasons in the preceding trial
3. Are pregnant, nursing, or planning pregnancy while enrolled in the study, or within 20 weeks after receiving the last dose of study medication.
4. Patients must agree not to receive a live virus or bacterial or BCG vaccination during the study or up to 12 months after the last administration of study drug.

5. Patients who have developed malignancy, or suspicion of active malignant disease during the preceding trial.
6. Are intending to participate in any other study using an investigational agent or procedure during participation in this study.
7. Cannot adhere to the concomitant medication requirements mentioned in [Section 4.2.2.](#)

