4.2.2.1 Restrictions regarding concomitant treatment (cont.)

Medications	Restriction time period
Systemic corticosteroids (eg, prednisone, budesonide)	
 Parenteral (SC, IM, or IV) or rectal corticosteroids are not permitted during the study and must not have been used within a 4-week period prior to visit 2. Oral corticosteroids must be at a prednisone-equivalent dose of ≤ 20 mg/day, or ≤ 6 mg/day of budesonide, and have been at a stable dose for at least 4 weeks prior to visit 2. If oral corticosteroids were recently discontinued, discontinuation must have been completed at least 3 weeks prior to visit 2.

Crohn's disease-specific antibiotics	If using a Crohn's disease-specific antibiotic for treatment of Crohn's disease, patients must have been using the antibiotic for at least 4 weeks before visit 2 at a stable dose. If not currently using a Crohn's disease-specific antibiotic, the stop date must have been at least 4 weeks prior to visit 2.
Opioids	Patients with regular daily opioid use over the past 3 months before screening are excluded due to the interference of such medication with key efficacy endpoints (CDAI)
Live or attenuated vaccines (during study or 140 days after last dose of study drug)	
• live attenuated influenza (intranasal)• herpes zoster• rotavirus• varicella (chicken pox)• measles-mumps-rubella (MMR) or measles mumps rubella varicella (MMRV)• oral polio vaccine (OPV)• smallpox• yellow fever• Bacille Calmette-Guérin (BCG)• oral typhoid

Tapering of corticosteroids

The tapering of prednisone dosage or equivalent (see [Appendix 10.2](#)) of other systemic corticosteroids is requested for patients achieving clinical remission the first time while on treatment with BI 655066. In such patients steroids must be tapered at a maximum rate of 2.5 mg per week to a dosage of 0. If a patient experiences a loss of clinical response (decrease in CDAI < 100 points from baseline on 2 consecutive visits) during steroid tapering, the dosage of prednisone may be increased back to the dosage used at study entry.

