6.2.3 End of trial and follow-up period

The follow up period is 20 weeks after the last administration of study medication. Refer to [Flow chart 1](#), [Flow chart 2](#) and [Flow chart 3](#) for further details.

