Section to be changed	Sections 3.3.2 – Inclusion Criteria and 3.3.3 - Exclusion Criteria
Description of change 10	Changed 15 to 20 weeks duration to remain on effective birth control after last dose of medication.
Rationale for change	To reflect updated safety risk language.
Section to be changed	Sections 4.1.6 – Packaging, labelling, and resupply
Description of change 11	Removed drug supplies being provided by BI. Added description of supplies.
Rationale for change	BI no longer provides the drug supplies. Other changes provided for clarity.
Section to be changed	Section 4.1.7 - Storage conditions
Description of change 12	Added language on proper storage and assessing any temperature excursions.
Rationale for change	Changes were made to provide more clarity.
Section to be changed	Section 4.1.8 - Drug accountability
Description of change 13	Added paragraph regarding unused medication.
Rationale for change	Moved paragraph from storage conditions to accountability as this is the proper section.
Section to be changed	Section 4.2.2.1 – Restrictions regarding concomitant treatment
Description of change 14	Added Live or attenuated vaccines 140 days after last study drug dose.
Rationale for change	Added to align with phase 3 protocols and due to product risk language.
Section to be changed	Section 5.1.1 – Efficacy endpoints
Description of change 15	Efficacy endpoints changed from Week 204/206/216 into 'by visit' time points.

[figure not shown]
Rationale for change	This study will be terminated and not all patients will have the same treatment duration. Using “by visit” will allow for the different time points when the patient will end treatment.
Section to be changed	Section 5.2.1 – Endpoints of safety
Description of change 16	Removed annual vital status for criteria for safety evaluation
Rationale for change	AbbVie standard does not require an annual vital status or follow up visit to occur after premature discontinuation.
Section to be changed	Section 5.2.2.1 – Adverse Event and Adverse Event of Special Interest
Description of change 17	Added language to define reporting elective surgery/procedures and language regarding cardiac events and procedures and TB.
Rationale for change	To capture further information on reporting requirements and for suspected cardiac events and TB.
Section to be changed	Section 5.2.2.2 – AE collection
Description of change 18	Removed language regarding annual vital status and reporting of SAEs and AESIs.

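### The protocol gives two post-dose restriction periods for live vaccines, 12 months in Section 3.3.3 and 140 days in Section 4.2.2.1, and does not say which governs

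*Protocol*

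**What the plan says.** Two operative parts of the protocol set a post-dose period for live vaccines.

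- **Section 3.3.3, criterion 4:** patients have to undertake to have no live viral, bacterial or BCG vaccine while on study, and the undertaking extends "up to 12 months after the last administration of study drug". This sits in a list introduced by the statement that a patient who meets any item may not roll over.
- **Section 4.2.2.1, table of restricted treatments:** "Live or attenuated vaccines (during study or 140 days after last dose of study drug". Ten vaccines follow, among them several live virus vaccines, oral typhoid and "Bacille Calmette-Guérin (BCG".

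The two parts are linked. Criterion 7 in Section 3.3.3 excludes patients who "Cannot adhere to the concomitant medication requirements mentioned in" Section 4.2.2, so the table's period is also part of eligibility.

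Two other places give context. Section 6.2.3 states: "The follow up period is 20 weeks after the last administration of study medication". Section 2.3 says that the drug, like other immune-modulating agents, could impair immune function and raise the risk of infection.

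**The concern.** The same class of vaccine carries two end dates in one protocol. Someone who consults the eligibility list finds 12 months; someone who consults the medication table finds 140 days. The rule is a safety instruction that patients carry out mostly after they have left the study, when no visit remains at which a misreading could be caught. What is at stake is whether patients who come off treatment, and those who look after them, have one unambiguous written rule.

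Criterion 4 is also drafted the wrong way round. It is phrased as a requirement under a heading where meeting an item bars entry, so on a literal reading a patient who agrees to the restriction would be excluded. This is a drafting slip, but it sits in the sentence that needs editing anyway.

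**Working it through.** The plan gives no figure to reproduce. The check sets the two rules side by side and converts units.

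**Inputs**

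| Item | Source | Value |
|---|---|---|
| Period A | Protocol 3.3.3, criterion 4 | 12 months after last administration |
| Period B | Protocol 4.2.2.1, vaccine row | 140 days after last dose |
| Follow-up after last dose | Protocol 6.2.3 | 20 weeks |
| Planned enrolment | Protocol 3.1 | about 60 patients |
| Latest concomitant-medication cut-off | SAP 7.3 | last dose + 140 days |

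**Step 1: do the rules cover the same vaccines?** Yes, at least in part. BCG is named in both. Criterion 4 covers live virus and bacterial vaccines by class, and the table lists vaccines of both kinds.

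**Step 2: size of the gap.** Taking 12 months as 365 days:

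- A - B = 365 - 140 = 225 days, that is, day 141 to day 365 after the last dose
- 225 / 7 = about 32 weeks
- A / B = 365 / 140 = about 2.6

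A leap year adds one day.

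**Step 3: position relative to follow-up.** 20 weeks x 7 = 140 days. Period B therefore ends with planned follow-up, and Period A runs about 225 days past it.

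**Step 4: does any passage decide between them?** None does. Criterion 7 brings Section 4.2.2 into the eligibility list without stating which period prevails.

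**Step 5: is it only a trace of superseded text?** No. Both statements stand in the current text. The amendment log, used here for context only, records under Amendment 4: "Added Live or attenuated vaccines 140 days after last study drug dose". For Section 3.3.3 the same amendment lists only the birth-control change from 15 to 20 weeks, with no change to criterion 4. An incomplete update is a plausible origin, but the contradiction does not depend on that.

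**Step 6: whom does it reach?** Section 3.1 lets patients who complete the study continue in M16-000 Sub-Study 3, and schedules the 140-day call for those who do not. Patients who roll over come under another protocol whose vaccine rules are not visible here. The gap clearly matters for those who stop without rolling over. Their number is not stated; it could be anything from none to all of the roughly 60.

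**Step 7: does an analysis depend on it?** Consider a vaccine given on day 200 after the last dose. SAP Table 7 defines LD as last dose plus 140 days and codes a medication started after LD as post-treatment. The period-specific rules below that table close the window at the same point, or earlier if the next treatment begins first. The vaccine is not concomitant under either protocol period. SAP Section 6.2 also keeps data collected beyond 140 days out of the analysis, and SAP Section 5.1 defines no per-protocol set that a late vaccination could affect.

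**The case against.** The strongest reply is that the two rules are not incompatible: a patient who observes the longer period has also observed the shorter one. The table says nothing after day 140, and silence does not authorise vaccination. That is correct, and it limits the finding to ambiguity over which period governs. It does not remove the ambiguity, because the protocol nowhere says that the two are to be read together in that way, and a reader of the table alone would stop at 140 days.

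Several stronger readings are tempting, and the documents do not support them:

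- **Sites tell patients conflicting things.** What patients are told cannot be seen, since the consent pages are not part of the material. Only the written rules can be shown to differ.
- **Every patient is exposed to the gap.** Those who enter M16-000 Sub-Study 3 move to another protocol.
- **Concomitant-medication coding or a deviation analysis depends on the choice.** The SAP's cut-off is independent of the vaccine rule. Protocol violation appears in SAP Section 8.1 only as a reason for stopping study drug, which cannot apply months after the last dose.
- **The 12-month undertaking is defective because follow-up ends at 140 days.** Criterion 4 asks for agreement at entry, not for a later assessment. The study cannot verify the last 225 days, but that alone is not an error.

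It is also fair to say that the inverted wording of criterion 4 would mislead few investigators. It carries little weight by itself.

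**Conclusion.** The point holds as an internal inconsistency: the protocol is wrong as written, because one safety restriction carries two durations and no order of precedence. The discrepancy is about 225 days, taking 12 months as 365 days and counting both periods from the last dose in this study. It applies to patients who stop treatment without entering M16-000 Sub-Study 3. The case for correcting it rests on clarity of a safety instruction alone; sample size and planned analyses are untouched. Nothing in the documents shows which of the two periods was intended, and no view is offered on which is right.

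**What to change.** Reconcile Section 3.3.3 criterion 4 and the vaccine row in Section 4.2.2.1 so that both state one post-dose period. The choice belongs to the sponsor's clinical team. In the same edit, reword criterion 4 so that it reads as an exclusion, in line with the heading above it. Check that the patient information, which could not be seen for this review, states the same period.

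The cost is a wording change in the protocol. The SAP needs no change, and no data collection or analysis is added.

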3.3.4 Removal of patients from therapy or assessments

3.3.4.1 Removal of individual patients

An excessive rate of withdrawals may render the study results uninterpretable; therefore unnecessary withdrawal of patients must be avoided. Patients who discontinue their treatment early should undergo all study required procedures including an early EoT visit and colonoscopy, as defined in [Section 6.](#)

Patients have the right to withdraw from the study at any time without the need to justify the decision.

The sponsor reserves the right to terminate a patient from the trial for non-compliance.

The investigator has the right to remove patients from the study for non-compliance.

Furthermore, patients' treatment must be discontinued early due to lack of efficacy (defined as an endoscopically confirmed CDAI re-increase to >100 points above baseline in 1311.6 and a CDEIS >4), or for other reasons (as described below). If, in the investigator's opinion, such a patient requires alternative medical therapy for their Crohn's disease, the study treatment must be stopped and patients may receive conventional treatment for active disease as per investigator's judgment.

Criteria and rules for stopping patient treatment due to reasons other than lack of efficacy include:

- Development of a toxicity or adverse event which warrants drug discontinuation.
- Development of any potentially life-threatening toxicity.
- Any concomitant illness that prevents compliance.
- The patient is unwilling to continue in the trial.

- Pregnancy in a female participant.
- Patient lost to follow-up despite reasonable efforts to make contact with the patient.
- Patient is no longer able to participate for other medical reasons (e.g., surgery, adverse events or other diseases).
- The DMC may recommend termination or re-design of the trial for other relevant issues of safety.

Patients who discontinue from the study after Visit 2 will be considered as "early discontinuations" and the reason for premature discontinuation must be recorded in the eCRFs. The data will be included in the trial database and will be reported.

3.3.4.2 Discontinuation of the trial by the sponsor

Abbvie Inc., reserves the right to discontinue the trial overall or at a particular trial site at any time for the following reasons:

1. Failure to meet expected enrolment goals overall or at a particular trial site,
2. Emergence of any efficacy/safety information that could significantly affect continuation of the trial, or any other administrative reasons, i.e. termination of clinical development of BI655066 in Crohn's disease,
3. Violation of GCP, the CTP, or the contract by a trial site or investigator, disturbing the appropriate conduct of the trial.

The investigator / the trial site will be reimbursed for reasonable expenses incurred in case of trial termination (except in case of the third reason).

4. TREATMENTS

4.1 TREATMENTS TO BE ADMINISTERED

BI 655066/ABBV-066 (risankizumab) will be administered intravenously and/or subcutaneously.

4.1.1 Identity of investigational product and comparator product(s)

The characteristics of the test product for i.v. administration are below.

Substance:	BI 655066/ABBV-066 (risankizumab): Anti-human IL-23p19 mAb
Pharmaceutical formulation:	
Chemical name:	Anti-human IL-23p19 mAb
Molecular weight:	Approximately 148 kDa
Source:	Boehringer Ingelheim Pharma GmbH & Co. KG
Unit strength:	
Dose (per infusion)	600 mg
Posology	3 infusions separated by 4 weeks
Route of administration:	i.v. infusions

The characteristics of the test product for s.c. administration are below.

Substance:	BI 655066/ABBV-066 (risankizumab): Anti-human IL-23p19 mAb
Pharmaceutical formulation:	
Chemical name:	Anti-human IL-23p19 mAb

Molecular weight:	Approximately 148 kDa
Source:	Boehringer Ingelheim Pharma GmbH & Co. KG
Unit strength:	
Dose (per injection)	180 mg
Posology	Every 8 weeks
Route of administration:	s.c.

4.1.2 Method of assigning patients to treatment groups

Patients directly rolled over from 1311.6 into this study will be assigned to open label s.c. treatment via IRT.

For early completers of 1311.6, i.e. patients who have completed 1311.6 qualifying for roll-over into 1311.20/M15-989 before availability of this study and not treated otherwise, will be assigned per clinical response post study treatment and at screening in 1311.20/M15-989 either to i.v. re-induction treatment or directly to open label s.c. treatment via IRT (as described earlier in [Section 3.1](#))

4.1.3 Selection of doses in the trial

Direct roll-over patients from 1311.6 will receive open label treatment with 180 mg s.c. q8w, representing the maintenance dose tested in phase II, that was found safe and effective in preceding study 1311.6.

Early completers of 1311.6 dependent on clinical response post study treatment and at screening in 1311.20/M15-989 will receive either 180 mg s.c. q8w maintenance treatment or re-induction with 3 infusions of 600 mg i.v. q4w followed by 180 mg s.c. q8w maintenance treatment.

4.1.4 Drug assignment and administration of doses for each patient

The dose of BI 655066/ABBV-066 (risankizumab) for s.c. and i.v. injections will be fixed.

The subcutaneous study drug will be administered as an injection in the abdomen, thighs, gluteal region, or upper arms. Injections being given in the same area should be at least 2 cm apart and should not be close to a vein. The injection site should avoid sites where the skin is tender, bruised, erythematous, or indurated, and should be alternated to other areas for subsequent doses.

Supplied BI 655066/ABBV-066 (risankizumab) solution for i.v. administration (concentration 10.0 mg/mL) will be injected into a 100 mL i.v. infusion bag of 5% dextrose in water (D5W) and administered as described in detail in the Investigator Site File (*Instructions for Preparation and Handling of BI 655066/ABBV-066 (risankizumab)*).

Subcutaneous administration of biologic agents involves the risk of local (injection site) or systemic hypersensitivity reactions. Therefore patients should be closely monitored for signs and symptoms of hypersensitivity reactions for approximately 30 minutes following study drug administration. Study personnel should observe the injection site for signs of redness, swelling or hardness. They should also ask subjects about itching, dizziness or shortness of breath. Patients should be advised that if they experience redness, swelling or other changes at the injection site, they should notify site personnel. They should further be advised that if they experience itching all over or a feeling of being swollen, dizzy or short of breath, they should notify site personnel or their own healthcare provider immediately.

The i.v. study drug will be administered under immediate supervision of the physician investigator or a designee with a minimum of a nursing degree. In all cases a physician

investigator must be on-site during administration and until at least 2 hours after the start of drug administration. Patients will remain at the trial center for approximately 1 hour following the end of i.v. administration (2 hours after the first administration)

Detailed procedures for preparing and handling of the study drug are provided in the ISF.

4.1.5 Blinding and procedures for unblinding

4.1.5.1 Blinding

Since this is a single group, open label study, there are no blinding issues and the dose received will be visible in the database.

4.1.5.2 Procedures for emergency unblinding

Not applicable.

4.1.6 Packaging, labelling, and re-supply

The clinical trial supply consists of containers (cartons) with trial- identification that hold the trial medication and is labelled as required per country requirements with the following:

- Trial number
- Name of product and strengths or identification code
- Pharmaceutical form
- Route and mode of administration
- Term "for clinical trial use" (domestic language)
- Sponsor name and address
- Storage conditions
- Medication number
- Batch number
- Expiry date (use-by-date)

Labels must remain affixed to the kits.

Drug supply and inventory will be controlled by IRT. Each kit label will contain a unique kit number. The kit is assigned to a subject via IRT at each dispensing visit. For details of packaging and the description of the label, refer to the ISF.

4.1.7 Storage conditions

Both i.v. and s.c. drug supplies will be kept refrigerated (the recommended storage conditions is +2 - +8°C or 36-46°F) in their original packaging. The trial medication must be stored securely, e.g., in a locked refrigerator or at a pharmacy and must be kept protected from light as well as must not be frozen at any time.

The refrigerator temperature must be recorded each business day. Malfunctions or any temperature excursion must be reported to the Sponsor immediately.

Study drug should be quarantined and not dispensed until AbbVie or AbbVie Temperature Excursion Management System (ATEMS) deems the drug as acceptable.

4.1.8 Drug accountability

Drug supplies, which will be provided by *the* sponsor, must be kept in a secure, limited access storage area under the storage conditions defined by the sponsor. Where necessary, a temperature log must be maintained to make certain that the drug supplies are stored at the correct temperature.

All unused medication must be returned to the sponsor. Receipt, usage and return must be documented on the respective forms in the ISF. An account must be given for any discrepancies.

The investigator / pharmacist / investigational drug storage manager will receive the investigational drugs delivered by the sponsor when the following requirements are fulfilled:

- approval of the study protocol by the IRB / ethics committee,
- availability of a signed and dated clinical trial contract between the sponsor and the Head of Trial Centre,
- approval/notification of the regulatory authority, e.g. competent authority,
- availability of the curriculum vitae of the principal investigator,

- availability of a signed and dated clinical trial protocol or immediately imminent signing of the clinical trial protocol, (in exceptional cases, medication could already be sent to the site, before its activation via IRT)
- if applicable availability of the proof of a medical licence for the principal investigator,
- for USA availability of the Form 1572.

The investigator / pharmacist / investigational drug storage manager must maintain records of the product's delivery to the trial site, the inventory at the site, the use by each patient, and the return to the sponsor or alternative disposition of unused product(s).

These records will include dates, quantities, batch/serial numbers, expiry ('use by') dates, and the unique code numbers assigned to the investigational product(s) and trial patients. The investigator / pharmacist / investigational drug storage manager will maintain records that document adequately that the patients were provided the doses specified by the CTP and reconcile all investigational product(s) received from the sponsor. At the time of return to the sponsor or appointed CRO, the investigator / pharmacist / investigational drug storage manager must verify that no remaining supplies are in the investigator's possession.

